#### 9.1.2.2. Setting for GBS etiology: Medical record review

The source population for the GBS etiology medical record review objective will be health plan members from approximately 3 regional integrated delivery systems. These systems have access to linked EHR and administrative billing data. The participation of the specific RPs, selected based in part on geographic representation, will be noted in the final SAP.

Individuals must meet all of the following inclusion criteria to be eligible for inclusion in this analysis:

- Research eligible at the participating RP;
- ≥18 years of age during the study period, January 2017 December 2024;
- Have ≥365 days of medical and pharmacy coverage preceding cohort entry, with gaps of ≤45 days permitted; and
- Meet the algorithm for incident GBS (outlined in Table 1).
- There are no exclusion criteria for this analysis.

• Diagnoses will be identified via billed ICD-10-CM diagnosis codes within the source data. Medical record review will be conducted via direct EHR access or medical records will be requested if necessary.

To ensure the subgroups of interest are included in the medical record review, there will be stratified random sampling within subgroups of eligible cases identified in the billing data. It is expected that all GBS cases with evidence of antecedent vaccination of any type (e.g., within 42 days) will be included in the medical record review as they are typically a minority of GBS cases. The balance of GBS cases without recent vaccination, which is expected to be the majority, will be randomly sampled to ensure adults <60 years of age with underlying conditions of interest (e.g., conditions associated with increased risk of RSV-LRTD) are included. Oversampling of more recent cases in 2023-2024 may be necessary. The number of charts sampled per subgroup will be decided upon after review of the distribution of the subgroups among GBS cases in the source population.

# 9.1.2.3. Setting for GBS etiology: Exploratory data mining-based signal detection

The source population for the data mining-based signal detection objective will be members from up to 3 national health plans. The participation of specific RPs will be noted in the final SAP.

Individuals must meet all of the following inclusion criteria to be eligible for inclusion in this analysis:

- Research eligible at the participating RP;
- $\geq$ 18 years of age during the study period, January 2017 December 2024;
- Have ≥365 days of medical and pharmacy coverage preceding cohort entry, with gaps of ≤45 days permitted; and
- Meet the algorithm for incident GBS (outlined in Table 1).
- There are no exclusion criteria for this analysis.

#### 9.1.3. Variables for Research Question 1

#### 9.1.3.1. Variables for GBS epidemiology and incidence

Subgroups of interest will include age (e.g., 18-59 years; ≥60 years), sex, comorbidities, recent vaccination, and region.

For the second objective in Research Question 1 – Describe individuals with GBS with respect to demographics, clinical characteristics, risk factors, treatment, and outcomes – variables of interest are listed in Table 2. The presence of underlying conditions that increase the risk of RSV-LRTD will be assessed, as well as evidence of certain antecedent infections that have been associated with GBS, such as COVID-19, influenza, other upper or lower respiratory tract infection, unspecified viral infection, gastrointestinal infections, and urinary

tract infections. . Recent antibiotic use, recent vaccination, or other preceding events that are risk factors for GBS may also be described.  Diagnostic testing for GBS (e.g., lumbar puncture, imaging) and treatment (e.g., intravenous immunoglobulin and plasma exchange) that is captured via codes in the data sources will be described.  Documentation of ICD-10-CM diagnosis code G65.0, sequelae of GBS, will be examined, as well as other diagnoses (e.g., muscle weakness), though common symptoms associated with GBS may not be coded.

Table 2. Variables expected to be included in descriptive analysis of incident, inpatient GBS cases

Variable	Notes
Demographics	
Age, age group	In years
Sex a	Male, Female, Ambiguous, Unknown
Race a	American Indian or Alaska Native, Asian, Black or
	African American, Native Hawaiian or Other Pacific
	Islander, White, Multiracial, Unknown
Hispanic ethnicity a	Yes, No, Unknown
Region	e.g., Census Bureau
Month-year of event	Dichotomous per month-year
Underlying conditions in 1-year prior to GBS diagno.	
Combined comorbidity index	Mean, standard deviation
	Categories $(0, 1, 2, \ge 3)$
Cardiovascular disease (e.g., heart failure, coronary artery disease, or congenital heart disease [excluding isolated hypertension])	Dichotomous
Chronic lung or respiratory disease (e.g., chronic obstructive pulmonary disease, emphysema, asthma, interstitial lung disease, or cystic fibrosis)	Dichotomous
End-stage renal disease or dependence on	Dichotomous
hemodialysis or other renal replacement therapy Diabetes	Dichotomous
Diabetes mellitus complicated by chronic kidney	Dichotomous Dichotomous
disease, neuropathy, retinopathy, or other end-organ damage, or requiring treatment with insulin or sodium-glucose cotransporter-2 inhibitor	Dichotomous
Neurologic or neuromuscular conditions causing impaired airway clearance or respiratory muscle weakness (e.g., poststroke dysphagia, amyotrophic lateral sclerosis, or muscular dystrophy [excluding history of stroke without impaired airway clearance])	Dichotomous
Chronic liver disease (e.g., cirrhosis)	Dichotomous
Chronic hematologic conditions (e.g., sickle cell disease or thalassemia)	Dichotomous
Severe obesity (body mass index ≥40kg/m²)	Dichotomous; Based on diagnosis codes, not measured height and weight
Moderate or severe immune compromise	Dichotomous; Based on diagnosis codes for specific conditions

Table 2. Variables expected to be included in descriptive analysis of incident, inpatient GBS cases

Variable	Notes
Frailty score	Based on Kim,  will be assessed in those 65 and
	older
Antecedent infections in 60 days prior to GBS diagno	
Respiratory infections	Dichotomous; e.g., COVID-19, influenza, otitis
	media, pneumonia, upper and lower respiratory tract
	infections
Gastrointestinal infections	Dichotomous; e.g., Campylobacter jejuni
Urinary tract infections	Dichotomous
Other infections	Dichotomous; e.g., Epstein-Barr virus, Zika virus,
TT (0.1.1.1.0.1.	septicemia P24.0
Unspecified viral infections	Dichotomous; e.g., B34.9
Vaccination within 42 days prior to GBS diagnosis b	
COVID-19 vaccination	Dichotomous
Influenza vaccination	Dichotomous
Meningococcal vaccination	Dichotomous
Pneumococcal vaccination	Dichotomous
RSV vaccination	Dichotomous
Tetanus-containing vaccination	Dichotomous
Zoster vaccination	Dichotomous
Other vaccinations	Dichotomous
Concurrent use of medication associated with	Dichotomous; e.g., antibiotics, anti-tumor necrosis
GBS	factor alpha
Symptoms / sequelae of GBS during hospitalization of	or in the 90 days after diagnosis
Sequelae of GBS (G65.0)	Dichotomous
ICU admission	Dichotomous; Based on diagnosis, procedure, and/or
	revenue codes, which may under-capture this care
Ventilation	Dichotomous; Based on diagnosis and/or procedure
	codes, which may under-capture this care
History of GBS >365 days prior to current	Yes/No; Ever in day -365 or earlier, based on
diagnosis	available enrollment
Evidence of concurrent pregnancy	Dichotomous
Care and testing received related to GBS during hosp	pitalization
Intravenous immunoglobulin	Dichotomous
Plasmapheresis	Dichotomous
Lumbar puncture	Dichotomous
Imaging (e.g., MRI)	

a. These are defined based on the Sentinel Common Data Model.

Note that nursing home residence, which is a factor associated with increased risk of severe RSV,  is not reliably identifiable in claims data.

The final variables will be specified in the SAP. Code lists for the variables listed above will be developed during SAP finalization. Some of the variables may be under-captured and therefore misclassified due to the nature of claims data.

b. Variables for vaccination within 21 days prior to GBS diagnosis will also be created.

# 9.1.3.2. Variables for GBS etiology: Medical record review

Abstraction and adjudication forms will be developed and finalized prior to medical record review start and variables to be collected during the review will be included in the SAP. In brief, date of symptom onset, diagnostic testing, symptoms, underlying conditions (e.g., those associated with increased risk of RSV-LRTD), antecedent infections, and other information needed for adjudication against the Brighton Collaboration case classifications will be recorded based on review of available records; see Table 3 for the classifications and criteria, as applied by Goud. Adjudicators will also assess the potential etiology of GBS among confirmed and possible cases per the Brighton Collaboration criteria based on the information available in the medical records.

# 9.1.3.3. Variables for GBS etiology: Exploratory data mining-based signal detection

# 9.1.3.3.1. Exposure for GBS etiology: Exploratory data mining-based signal detection

One exposure tree will be developed with top-level categories of vaccines, drugs, and infections. This tree, with hierarchal branches, will allow for the detection of potential associations with GBS on both a specific and group level.

Individuals will be permitted to have multiple exposures if the exposure incidence criteria are met. Rules to define an incident exposure will be included in the SAP. If an individual receives multiple exposures within the same branch of the tree on the same day, then only one of those exposures will be included in the analysis. In this situation, the exposure with the smallest count of unique users over the study period will be retained to increase numbers for the rarer exposures.

# 9.1.3.3.2. Outcome for GBS etiology: Exploratory data mining-based signal detection

GBS will be identified in claims data using the algorithm detailed in Table 1. Alternative case-finding algorithms may be used in sensitivity analyses, which will be specified in the SAP.

#### 9.1.4. Data Sources for Research Question 1

#### 9.1.4.1. Data Sources for GBS epidemiology and incidence

These analyses will be conducted using health plan administrative claims data held by up to 3 national health plans (e.g., Carelon, Humana, and CVS Health). These RPs participate in the US FDA's Sentinel System. Other RPs may be included and final participating sites will be specified in the SAP.

The FDA Sentinel System, established under the Sentinel Initiative,  uses electronic healthcare data from a distributed data network for monitoring the safety of regulated medical products in the US. Sentinel RPs use the Sentinel Common Data Model (SCDM) to standardize demographic and clinical data elements. 

In addition to providing claims data for the analysis, the RPs will provide scientific input and feedback to support this study. For this analysis, the most recently available data refreshed

for the Sentinel System will be leveraged if possible, or sites will create a study-specific refresh as needed.

#### 9.1.4.2. Data Sources for GBS etiology: Medical record review

The GBS etiology medical record review objective will be conducted using administrative billing data from approximately 3 regional integrated delivery systems, or other appropriate data sources, with geographic diversity. Where applicable, administrative billing data that has been converted into the SCDM will be used for this objective. EHRs from within each RP will primarily be used for abstraction, review, and adjudication of the identified cases; if cases are seen at hospitals outside of the RP, charts may be requested.

# 9.1.4.3. Data Sources for GBS etiology: Exploratory data mining-based signal detection

The GBS etiology data mining-based signal detection objective will be conducted using health plan administrative claims data held by up to 3 national health plans (e.g., Carelon, Humana, and CVS Health). These RPs participate in the US FDA's Sentinel System. In addition to providing claims data in the SCDM, the RPs will provide scientific input and feedback to support this study.

#### 9.1.5. Study Size for Research Question 1

Data on all individuals meeting the applicable eligibility criteria within the contributing RPs will be analyzed for the GBS epidemiology and incidence objectives, and the data mining-based signal detection objective.

For the first 2 objectives, where we will estimate the incidence of GBS and describe individuals with GBS, the national health plans expected to participate in these analyses have provided preliminary counts of inpatient, incident GBS:  $\geq 1,000$  GBS cases among those 18-59 years of age and  $\geq 2,000$  among those 60 and older.

The medical record review objective will be conducted on approximately 300 cases.

#### 9.1.6. Data Management for Research Question 1

Please see Section 9.2.6 for Data Management details for the full study.

#### 9.1.7. Data Analysis for Research Question 1

Detailed methodology for summary and statistical analyses will be documented in the SAP, which will be dated, filed, and maintained by the sponsor. The SAP may modify the plans outlined in the protocol; any major modifications of primary endpoint definitions or their analyses would be reflected in a protocol amendment.

When appropriate, publicly available Sentinel analytic tools will be used for analyses. Modifications to the tools, when used, may be needed to meet study objectives, in which case the SAS programming data quality assurance (QA) standard operating procedures will be followed (see Figure 3). All statistical calculations will be performed using SAS 9.4 or higher.

# 9.1.7.1. Data Analysis for GBS epidemiology and incidence

Descriptive statistics of adults 18 and older with GBS in 2017 through 2024 will be reported via frequencies and percentages for discrete variables and, for continuous variables, either means and standard deviations or medians and interquartile ranges. The incidence rate of GBS, and corresponding 95% CIs, will be estimated overall and for several subgroups, as described in Section 9.1.1.1, showing how and to what degree incidence rates vary across groups and whether there have been changes in rates during the study period.

#### 9.1.7.2. Data Analysis for GBS etiology: Medical record review

Demographic and clinical characteristics of members with algorithm-defined GBS will be summarized using descriptive statistics (e.g., means and standard deviations or medians and interquartile ranges for continuous variables and frequencies and percentages for discrete variables).

Once all medical records are reviewed and adjudicated, the data will be combined across RPs and the PPV for GBS will be calculated as:

PPV = members with chart-confirmed GBS, among those with algorithm-defined GBS \*100 members with algorithm-defined GBS with complete charts

The PPV of confirmed and possible GBS cases combined will also be calculated.

PPVs will be calculated by age group (e.g., 18-59 and ≥60 years), evidence of antecedent infection, evidence of recent vaccination, and presence of conditions putting individuals at increased risk of RSV-LRTD. Ninety-five percent CIs for PPVs will be calculated.

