neurologist will be reviewed. If no appointment with a neurologist occurs within approximately 60 days, the first ambulatory encounter post hospitalization will be included in the review. Trained abstractors, or the adjudicators themselves, at each participating RP will extract information from the applicable inpatient and ambulatory records into a structured form or database equivalent (e.g., REDCap). Information will be collected from medical record elements / sections including admission notes, discharge summaries, laboratory test results, radiographic reports, specialist consultation notes, progress notes, and applicable treatments administered. The abstracted information and corresponding records will be reviewed by a clinician, preferably a neurologist, within each RP who will use the study's case definitions for GBS to adjudicate whether a case is confirmed, possible, or not GBS. 1,2 If a neurologist is unavailable, an alternative clinician will conduct the adjudication; training in the adjudication of GBS by a neurologist will be provided if possible. Adjudicators will be asked to assess what they think the cause of GBS was (e.g., infection, vaccination) based on the available information. The database used for abstraction and adjudication will be maintained by each RP and only deidentified data (e.g., relativized dates) will be shared with the Harvard Pilgrim Health Care Institute (HPHCI) for analysis. Aggregate data will be shared externally, including with Pfizer and FDA.

The PPVs and corresponding 95% confidence intervals of the GBS algorithm will be calculated overall and within subgroups for confirmed cases only, and for confirmed and possible cases combined.

Descriptive information will be summarized for diagnoses and care received during hospitalization. The potential cause of GBS, pre-existing conditions, and preceding events will also be summarized for confirmed and possible cases. Where records from preceding ambulatory care are available, information on diagnostic testing and results for antecedent infection, for example, will be reported.

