# 9.1.9.2. Limitations of GBS etiology: Medical record review

There are potential limitations of the research methodology and data sources for this objective. First, members within the RPs, which are expected to be integrated delivery systems, may not be representative of the general population and findings from their data may not be representative of patient care in other settings.

PPVs will be calculated for the GBS algorithm overall and within important subgroups. Because stratified sampling will be done to ensure representation of the groups of interest, the PPV estimates may have wide 95% CIs. In addition, this study is not designed to calculate sensitivity or specificity of the algorithms.

Identification of the etiology of GBS, among those identified as confirmed or possible cases, may be challenging. Identifying antecedent infections or other preceding events requires documentation in the medical record, and diagnostic testing for many infections is uncommon. Clinician adjudicators may not have the information available to make the case and/or the etiologic determination.

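### The chart review is expected to take every recently vaccinated GBS case but only a sample of the rest, so pooled, unweighted summaries of cause and preceding events would overstate vaccination by a factor of N/300

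*Protocol*

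**What the plan says.** **Selection.** On recently vaccinated cases, Protocol Section 9.1.2.2 says "It is expected that all GBS cases with evidence of antecedent vaccination of any type (e.g., within 42 days) will be included". On the others it says "The balance of GBS cases without recent vaccination, which is expected to be the majority, will be randomly sampled", with the aim of bringing in adults under 60 with underlying conditions. It adds that "Oversampling of more recent cases in 2023-2024 may be necessary". Stratum sizes are left open: "The number of charts sampled per subgroup will be decided upon after review of the distribution of the subgroups". Section 9.1.1.2 also names age, risk factors, recent infection and calendar time as sampling factors. The review covers about 300 cases (Section 9.1.5).

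**Summary.** Section 9.1.1.2 states: "The potential cause of GBS, pre-existing conditions, and preceding events will also be summarized for confirmed and possible cases". Section 9.1.3.2 says where cause comes from: "Adjudicators will also assess the potential etiology of GBS among confirmed and possible cases". Section 9.1.7.2 states: "Demographic and clinical characteristics of members with algorithm-defined GBS will be summarized using descriptive statistics", with frequencies and percentages for discrete variables. The Abstract (Section 4, data analysis for Research Question 1) counts recent vaccination, antecedent infection and underlying conditions among those characteristics, and describes the table as covering cases in the sample. Only the PPV is broken down by vaccination, infection, age and risk condition.

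**Stated limitation.** On the effect of the sampling, Section 9.1.9.2 says: "Because stratified sampling will be done to ensure representation of the groups of interest, the PPV estimates may have wide 95% CIs". It does not mention bias in pooled summaries.

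**The concern.** Recent vaccination is one of the candidate causes that the review is meant to identify, and it also determines which charts are drawn. When selection depends on a factor, the raw percentage with that factor among the selected cases reflects the design, not GBS in the source population. The same applies to anything associated with the selection factors, including attributed cause, underlying conditions, age and calendar year.

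At stake is the share of GBS judged to be caused by vaccination in a post-marketing vaccine safety study. The rationale (Section 7) says that a better understanding of GBS and its preceding risk factors should put GBS risk after vaccination in context. The chart review is the only component that yields an adjudicated cause. A pooled table read as a description of GBS cases would overstate the vaccination share even with perfect adjudication.

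**Working it through.** **Inputs**
- Charts reviewed, n: about 300 (Section 9.1.5).
- Sampling fraction for recently vaccinated cases: 100%, as expected in Section 9.1.2.2.
- Sampling fraction for the remaining cases: below 100%, value not stated.
- Eligible cases in the roughly 3 integrated delivery systems, N: not stated. The counts in Section 9.1.5 (at least 1,000 aged 18-59 and at least 2,000 aged 60 and over) belong to the national health plans, so they cannot be used for N.
- True share recently vaccinated, v: not stated beyond being a minority. 10% is used below for illustration.

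The protocol gives no derivation of the 300 and no expected vaccinated share, so there is no figure of its own to reproduce.

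**Unweighted share**

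Vaccinated cases in the sample = vN. Unweighted share = vN/300. Inflation = (vN/300)/v = N/300, whatever v is, provided vN does not exceed 300.

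| N (assumed) | Vaccinated charts at v = 10% | Sampling fraction for the rest | Unweighted share | Inflation |
|---|---|---|---|---|
| 300 | 30 | 270/270 = 1.00 | 10.0% | 1.00 |
| 400 | 40 | 260/360 = 0.72 | 13.3% | 1.33 |
| 600 | 60 | 240/540 = 0.44 | 20.0% | 2.0 |
| 900 | 90 | 210/810 = 0.26 | 30.0% | 3.0 |

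**Attributed cause**

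Suppose a fraction a of vaccinated cases is judged vaccine-caused, and no unvaccinated case is. The sample share is a·vN/300 against a true a·v, so the factor is again N/300. This requires a to be the same in the sample as in the source, which holds because all vaccinated cases are taken.

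**Restriction to confirmed and possible cases**

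The cause summary drops cases adjudicated as not GBS. Take N = 600 and v = 10%, with an assumed 70% of vaccinated and 80% of other cases retained.
- True share: 42/(42 + 432) = 8.9%.
- Sample share: 42/(42 + 192) = 17.9%.
- Factor: 2.03.

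With the two percentages swapped the factor is 1.97. At N = 900 the corresponding range is 2.92 to 3.08. Unequal PPV therefore changes the result little.

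**Effect of weighting**

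Weight each chart by eligible/reviewed in its stratum. At N = 600, vaccinated charts have weight 60/60 = 1 and the others 540/240 = 2.25. The weighted share is 60/(60 + 240 × 2.25) = 60/600 = 10%, the true value. The same recovery holds at the other values of N.

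**Scale of N**

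At the protocol's 2 cases per 100,000 person-years over the 8 years 2017-2024, N = 300 needs 300/(0.00002 × 8) = 1.9 million adult members. N = 600 needs 3.75 million and N = 900 about 5.6 million. Membership is not stated, and that rate is given for people aged 18-59 at increased risk, so this is only an order of magnitude.

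**The case against.** The strongest reply is that the protocol is silent on weights and does not rule them out. Section 9.1.7 leaves detailed methodology to the SAP, and the sampling fractions do not exist yet. That is fair as far as it goes. But the protocol itself fixes a sampling rule that selects on a candidate cause and a summary over the reviewed cases, with stratification specified only for the PPV. Those two elements do not fit together. Valid weights also need eligible and reviewed counts recorded per stratum when charts are drawn, so the requirement belongs with the sampling plan.

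Several other replies stand in part:
- Frequencies and percentages are specified for demographic and clinical characteristics. For potential cause the protocol says only that it will be summarised. A reader might infer that cause is explicitly planned as a plain percentage, but the text does not say so.
- The Abstract describes the table as covering cases in the sample, and describing a sample as a sample is legitimate. The difficulty arises once the figures are read as describing GBS cases, as the phrase members with algorithm-defined GBS in Section 9.1.7.2 invites.
- The claims-based epidemiology objective records vaccination within 42 days for all identified cases, unsampled (Table 2). The share preceded by vaccination is therefore available without this bias, chiefly from the national plans. It gives no adjudicated cause.
- Research Question 2 takes only PPVs from the chart review, so this bias does not carry into the self-controlled risk interval analysis.
- The sentence in Section 9.1.9.2 on wide PPV intervals is true. It is incomplete, not wrong.

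**Conclusion.** The point holds in mechanism and direction. If the sampling is carried out as described and the reviewed cases are pooled without weights, the share with recent vaccination is too high by N/300. The share attributed to vaccination is too high by the same factor if the attribution rate is unchanged. Upward bias for vaccination follows whenever there are more eligible cases than charts, which the sampling plan presupposes.

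The size is conditional. A reader might infer a several-fold inflation, but the protocol does not support that as a fact, because N for the integrated systems is not given. The factor ranges from none at N = 300 to 2-fold at N = 600, and 3-fold needs N of at least 900.

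A reader might also infer that infection, older cases and earlier years are necessarily understated. That does not follow. Recent infection is itself a listed sampling factor, and oversampling of 2023-2024 is only a possibility. Those shares are also set by the design, in a direction that depends on the final strata.

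**What to change.** In Section 9.1.7.2, state that pooled chart-review percentages meant to describe GBS cases (cause, preceding events, underlying conditions) are weighted by the inverse of the stratum- and research-partner-specific sampling fraction, with design-based 95% CIs. Alternatively, state that they are reported only within sampling strata. In Section 9.1.2.2, require the eligible and reviewed counts to be recorded for each stratum and research partner when charts are drawn. In Section 9.1.9.2, add that unequal sampling biases unweighted pooled summaries, alongside the existing remark on wide PPV intervals.

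No new data are needed, because the fractions are known by design once the strata are set. The cost is wording, some record-keeping and somewhat wider intervals for the weighted percentages.

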#### 9.2.3.2.2. Outcome for SCRI

GBS will be identified in claims data using the algorithm detailed in Table 1. This study will include GBS cases during the risk and control windows among people who die during follow-up. Deaths will be captured via enrollment data (for both in-hospital and out-of-hospital deaths) and hospital discharge status (for hospital deaths); death capture is expected to be incomplete, as is typically the case with death data from administrative claims data in the US. Follow-up time will artificially *not* be censored at the time of death. In other words, an eligible individual who has a GBS case during the risk or control windows and dies will still contribute to the full risk and control windows.

If the SCRI study commences due to completion of 4 RSV seasons with no statistically significant positive association between ABRYSVO and GBS from the RCA, GBS cases will not be confirmed via medical record review, but rather results will be adjusted using the PPV of the GBS algorithm produced in Research Question 1. If the SCRI study commences due to a statistically significant finding from an RCA, medical record review of GBS cases in the SCRI study will be conducted as part of the signal evaluation. However, a limitation of medical record review is that not all medical records will be retrievable. For the GBS cases where medical records cannot be retrieved, results will be adjusted using the PPV of the GBS algorithm. For example, if medical records cannot be retrieved for 10 GBS cases and the PPV for the GBS algorithm is 80%, this will be readjusted to 8 GBS cases.

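### The PPV formula is an unweighted count ratio, but charts are sampled with deliberately unequal fractions, so the overall and mixed-subgroup PPVs reflect the chart mix if PPV differs between strata

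*Protocol*

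**What the plan says.** Protocol Section 9.1.5 sets the size of the chart review: "The medical record review objective will be conducted on approximately 300 cases". Section 9.1.2.2 describes stratified random sampling of algorithm-defined cases. For one stratum the sampling is close to a census: "It is expected that all GBS cases with evidence of antecedent vaccination of any type (e.g., within 42 days) will be included". The remaining cases, expected to be the majority, are sampled at random in a way meant to secure adults under 60 with conditions of interest. On calendar time: "Oversampling of more recent cases in 2023-2024 may be necessary". The number of charts per subgroup is set later, once the subgroup distribution has been seen.

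Section 9.1.7.2 then fixes the estimator. After adjudication, "the data will be combined across RPs and the PPV for GBS will be calculated as" a ratio with numerator "members with chart-confirmed GBS, among those with algorithm-defined GBS" and denominator "members with algorithm-defined GBS with complete charts". No sampling weight or standardisation appears. Under Section 9.1.1.2 the PPVs "will be calculated overall and within subgroups for confirmed cases only, and for confirmed and possible cases combined". The planned subgroups are age group, antecedent infection, recent vaccination and RSV-risk conditions.

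Section 9.1.9.2 gives wide intervals as the only consequence of the stratified sampling for the PPVs. Section 9.1.1.2 says it is unclear whether PPV varies with underlying conditions or with antecedent events such as vaccination or infection, and cites published PPVs from 24% to 82%.

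For the SCRI without a prior signal, Section 9.2.3.2.2 states that "results will be adjusted using the PPV of the GBS algorithm produced in Research Question 1". The Abstract (outcome for the SCRI) and Section 9.2.7.2.2 use the plural. Section 9.2.7.2.3 adds a secondary analysis with different PPVs in the two windows.

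**The concern.** A pooled count ratio estimates the PPV among source cases only if every case had the same chance of review, or if PPV is the same in every stratum. The first condition is excluded by design. The second is one of the questions the review is meant to answer.

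Followed as written, Section 9.1.7.2 gives an overall PPV whose target depends on an allocation chosen later. The 18-59 PPV has the same difficulty, because it combines a fully reviewed vaccinated stratum with partly reviewed others. The PPV in cases without recent vaccination mixes the fractions used for age, conditions and calendar time. Only a stratum sampled at a single fraction, such as recently vaccinated cases if all are taken, is free of the problem.

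At stake are the headline result of the validation objective and, depending on which PPV is used, the absolute-risk output of the SCRI.

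**Working it through.** **The plan's own figure.** Sections 9.2.3.2.2 and 9.2.7.2.2 turn 10 unretrieved cases at a PPV of 80% into 8 cases: 10 × 0.80 = 8. This reproduces.

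**Inputs from the protocol.** About 300 charts; recently vaccinated cases expected in full; others sampled; unweighted ratio.

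**Inputs not in the protocol (assumed).** Eligible cases N = 400, 600 or 1,000; recently vaccinated share v = 5%, 10% or 20%; PPVs PV (vaccinated) and PU (others).

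**Formulas.** Vaccinated charts nV = N × v; other charts nU = 300 − nV.
- Raw PPV (Section 9.1.7.2) = (nV × PV + nU × PU) / 300
- Weighted PPV = v × PV + (1 − v) × PU
- Difference = (nV/300 − v) × (PV − PU)

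The difference vanishes if either factor is zero, that is, with equal sampling or homogeneous PPV.

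| N | v | nV | nU (fraction of others) | PV / PU | Raw | Weighted | Raw − weighted (points) |
|---|---|---|---|---|---|---|---|
| 400 | 5% | 20 | 280 (74%) | 70% / 80% | 79.3% | 79.5% | −0.2 |
| 400 | 5% | 20 | 280 (74%) | 60% / 80% | 78.7% | 79.0% | −0.3 |
| 600 | 10% | 60 | 240 (44%) | 60% / 80% | 76.0% | 78.0% | −2.0 |
| 600 | 20% | 120 | 180 (37.5%) | 60% / 80% | 72.0% | 76.0% | −4.0 |
| 1,000 | 20% | 200 | 100 (12.5%) | 60% / 80% | 66.7% | 76.0% | −9.3 |
| 1,000 | 20% | 200 | 100 (12.5%) | 90% / 75% | 85.0% | 78.0% | +7.0 |
| any | any | – | – | 80% / 80% | 80.0% | 80.0% | 0 |

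Worked line, N = 600 and v = 10%: (60 × 0.60 + 240 × 0.80) / 300 = 0.760, against 0.10 × 0.60 + 0.90 × 0.80 = 0.780.

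For scale, a simple binomial 95% half-width at 300 charts and a PPV of 78% is 1.96 × √(0.78 × 0.22 / 300) = 0.047, or 4.7 points. The same formulas apply within ages 18-59, with N, v and the number of charts read within that age group.

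**SCRI, no charts reviewed.** Take for illustration 6 risk-window and 2 control-window cases, equal 42-day windows and 2.0 million doses. With one PPV p in both windows, the rate ratio is 6p / 2p = 3.0 at any p. The attributable risk is (6p − 2p) / 20 per 100,000 doses: 0.140, 0.152 and 0.160 at p = 70%, 76% and 80%.

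**SCRI after a signal.** Confirmed cases count 1 and unretrieved cases count p, so p need not cancel. With 6 confirmed and 2 unretrieved in the risk window, and 2 and 2 in the control window, the rate ratio is (6 + 2p) / (2 + 2p): 2.16 at p = 0.72 and 2.12 at p = 0.78.

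**The case against.** The strongest reply is that Section 9.1.7.2 merely defines a PPV, that Section 9.1.7 leaves detailed methods to the SAP and lets it modify the protocol, and that weights cannot be written down before the allocation is known. This stands in part: the weight values must wait. The rule does not have to wait, and this is more than an omitted detail, because the protocol writes out an estimator that does not match its own sampling plan and treats the sampling as a matter of precision only.

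It is also fair that the bias is conditional. A reader might infer that the reported PPV will certainly be biased. The documents do not support that: they say variation in PPV is unclear, and the 2023-2024 oversampling is only possible. A reader might also infer that the intervals assume simple random sampling, but no interval method is named.

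A further tempting inference is that the biased overall PPV becomes the SCRI correction factor and distorts the SCRI result. No section fixes the overall PPV for that role; the wording is singular in one place and plural in others. Where no charts are reviewed, a common PPV leaves the rate ratio unchanged.

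Finally, weighting does not give the PPV that the SCRI needs. Every SCRI case is an ABRYSVO vaccinee. With assumed PPVs of 60% and 80%, the raw values in the table lie nearer to the vaccinated PPV than the weighted ones. A weighted all-case 18-59 PPV would lean towards mostly unvaccinated cases. This objection stands in full and limits the remedy to the validation objective.

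**Conclusion.** The point holds as a mismatch between sampling plan and estimator. If PPV differs between sampling strata, the overall and mixed-subgroup PPVs of Section 9.1.7.2 estimate the chart mix and not the algorithm's PPV in the source cases, and Section 9.1.9.2 does not say so.

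The size cannot be determined from the protocol, which gives neither the number of eligible cases in the integrated delivery systems nor the stratum shares or stratum PPVs. Under the assumptions above, with stratum PPVs of 60-90%, the gap runs from about 0.2 to 9 points in either direction. It is small when most eligible cases are reviewed and zero when PPV is homogeneous. The larger gaps require many eligible cases and a large vaccinated share.

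For the SCRI, the finding is that the PPV to be used is not clearly identified. In the no-signal path, one common PPV affects attributable risk and case counts. The rate ratio can move only if charts are partly retrieved (by 0.04 in the example) or if window-specific PPVs are used.

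**What to change.** 1. In Section 9.1.7.2, compute the overall PPV and every subgroup PPV that mixes strata with inverse-sampling-fraction weights: eligible cases in the stratum divided by completed charts in the stratum, by research partner. Use design-based 95% confidence intervals. Report single-stratum PPVs unweighted.
2. In Section 9.1.9.2, add that unequal sampling biases unweighted pooled PPVs if PPV differs between strata.
3. Reconcile the singular in Section 9.2.3.2.2 with the plural in the Abstract and Section 9.2.7.2.2, and name the PPV that enters the SCRI. It should be the one that best matches vaccinated cases aged 18-59, such as the recent-vaccination stratum PPV for the risk window, and not the weighted all-case 18-59 PPV. Control-window cases (days 43-84) fall outside a 42-day recent-vaccination stratum, so the PPV for that window also has to be stated.

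The cost is low. The stratum counts are known once the sample is drawn and the charts are completed, no further charts are needed, and the intervals become slightly wider.
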